Some research has focused on possible relationships between gingivitis and other diseases or conditions. For example, bleeding, which has long been identified as an important objective sign of gingival inflammation, is recognized as a risk factor for progressive periodontal disease and tooth loss.  Various health conditions have been implicated in the natural history of gingivitis. Along with plaque accumulation, other conditions like pregnancy, diabetes and immune deficiency have been shown to modulate the clinical expression of gingivitis.  Endogenous hormones are believed to play a role in plaque-associated gingivitis seen during puberty, menstruation and pregnancy.  The latter, "pregnancy gingivitis", has long been recognized as archetypical with respect to the clinical characterization of gingivitis. In clinical research, pregnant women are reported to experience approximately a 20% increase in plaque and gingivitis beginning in the late first trimester, which persists or worsens during pregnancy, and returns to baseline after delivery without other interventions. 

While pregnancy is recognized to contribute to clinical gingivitis, studies evaluating possible relationships between periodontal disease and pregnancy outcomes have equivocal results. Early research from a case control study among 124 pregnant women in North Carolina, USA identified periodontal disease extent and severity as a significant risk factor for preterm low infant birth weight. Several epidemiological and intervention studies followed, and meta-analysis of this complex research initially supported a role for periodontal treatment in reducing adverse pregnancy outcomes (birth weight or prematurity). Subsequently, a few high-quality clinical trials have specifically evaluated the role of intensive periodontal intervention (usually scaling and root planing) on pregnancy outcomes. These

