## 4. Inclusion Criteria

In order to be included in the study, each subject must:

- provide written informed consent prior to participation and be given a signed copy of the informed consent form;
- be at least the age of legal consent;
- be between 8 and 24 weeks of pregnancy;
- have at least 20 natural teeth:
- have moderate-to-severe gingivitis during pregnancy, including at least 30 intraoral sites with evidence of marginal gingival bleeding.

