6.0. Statistical Methods and Determination of Sample Size

All statistical tests will be 2-sided tests except where noted; and any treatment difference p-values less than 0.05 will be cited as statistically significant. The analysis for the evaluable population will be considered as the primary population and the Intent-to-Treat (ITT) analyses will be considered secondary.

The primary test will be the treatment effect test for 3-month change from baseline for Löe-Silness. No adjustments for multiple testing will be employed.

All statistical tests will be carried out using SAS® version 9 (SAS Institute Inc., Cary, NC).

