6.3 Gingivitis Endpoints

Null Hypothesis: There is no difference between treatment groups with respect to the mean gingivitis change from baseline when an adjustment is made for the respective baseline gingivitis score and other demographic parameters.

Alternative Hypothesis: There is a difference between treatment groups with respect to the mean gingivitis score change from baseline when an adjustment is made for the respective baseline gingivitis score and other demographic parameters.

Statistical analyses for gingivitis efficacy endpoint will be based on whole-mouth average Löe-Silness change from baseline scores (Baseline score minus post treatment score) and will be considered the primary variable, with Month 3 the primary time point of interest. An analysis of covariance (ANCOVA) will be performed to determine treatment differences on the whole mouth average gingivitis reduction scores with the baseline gingivitis score as the covariate and also including study site, treatment, and the interaction of site and treatment as factors in the model. The interaction of treatment with the covariate will also be assessed for significance. If the interactions are not significant at the 10% level then they will be eliminated from the final model.

Additionally, 95% confidence intervals will be generated on the treatment difference for the average change from baseline scores. Separate analyses will be performed for each visit. The within-treatment difference from baseline gingivitis score will also be tested versus zero for each visit using the adjusted means from the ANCOVA model

The same analyses will also be generated for the reduction of Total Number of Bleeding sites and Pocket Depth reduction from baseline at each visit.

Testing for normality of the gingivitis endpoints will be carried out using Shapiro-Wilk test and residual plots. For non-normal data, a transformation such as taking the natural log (e.g., Total Number of Bleeding Sites) will be implemented or a non-parametric analysis will be carried out.

In addition to the ITT and Evaluable populations, the GI analysis will be carried out on the Intent-to-Treat subjects without examiner #129 data.

Additional subgroups may be defined for analysis on the gingivitis data, such as the following:

- By Study Site
- Subjects who had the same examiner for Baseline exam as for their post-baseline exam
- Subjects with the highest (top 50%) and Lowest (lowest 50%) Number of Bleeding Sites at Baseline

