- By Age (< median age vs. ≥ median age)
- Subjects who completed all monthly visits
- By Gestational Age at enrollment (8 to ≤12 weeks, >12 to ≤16 weeks, >16 to ≤20 weeks, >20 to ≤24 weeks)

Oral Hygiene questionnaire data will be summarized by treatment group at Baseline and Month 3 visits.

Additional analyses may also be performed in order to more fully understand the data.

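### The primary Löe-Silness ANCOVA omits gestational age at enrolment, a collected and plausibly prognostic baseline value; the cost is a modest loss of precision, and the SAP's hypothesis wording does not match its model

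*SAP*

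**What the plan says.** - **Primary test.** SAP 6.0: "The primary test will be the treatment effect test for 3-month change from baseline for Löe-Silness". Tests are two-sided ("All statistical tests will be 2-sided tests except where noted") and "any treatment difference p-values less than 0.05 will be cited as statistically significant".
- **Model.** SAP 6.3 fits an ANCOVA on the change score "with the baseline gingivitis score as the covariate and also including study site, treatment, and the interaction of site and treatment as factors". A treatment-by-baseline interaction is also checked, and interactions not significant at the 10% level are removed. Protocol section 18 has the same covariate and the same site factor.
- **Hypotheses.** SAP 6.3 states both hypotheses "when an adjustment is made for the respective baseline gingivitis score and other demographic parameters". Protocol section 17 mentions adjustment for the baseline Löe-Silness score only.
- **Entry window.** Protocol section 4 requires each woman to "be between 8 and 24 weeks of pregnancy".
- **Randomisation.** Protocol section 10 balances, within site, on preterm-birth history, smoking and number of bleeding sites (below 60, or 60 and above). Entry week is not a factor.
- **Data.** SAP 5.1 lists last menstrual period, estimated delivery date, and first ultrasound date with its gestational age reading among the baseline obstetrical variables.
- **Background.** Protocol section 1 reports "approximately a 20% increase in plaque and gingivitis beginning in the late first trimester, which persists or worsens during pregnancy".
- **Present use.** In SAP 6.3, "By Gestational Age at enrollment" (four categories) is one of several gingivitis subgroups that may be analysed.

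**The concern.** The primary outcome is a three-month change in gingivitis measured during pregnancy, and the women start that period up to 16 weeks apart. If gingivitis begins to rise late in the first trimester, a woman who enters at week 8 to 10 may pass through the onset during follow-up, while one who enters at week 22 to 24 may already carry it at baseline. Two women with the same baseline score could then have different expected changes. The baseline score cannot fully separate habitually high gingivitis from gingivitis raised by pregnancy, so adjusting for it may capture only part of the stage effect.

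What is at stake is precision: residual variance that a value already on file could remove. There is also a prespecification issue. The SAP's hypotheses refer to further adjustment without saying for what, which leaves room to choose covariates after the results are seen.

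**Working it through.** **Inputs from the documents** (Protocol section 11, SAP 6.8): 300 per group, difference 0.05, variability 0.185, two-sided alpha 0.05, power at least 90%. I read 0.185 as the residual SD of the planned model; the documents do not say whether it is.

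**Inputs the documents do not give (assumed):**
- Partial R² of entry week with the Month 3 change, given baseline score and site: 0 to 0.10.
- Distribution of entry week: uniform over weeks 8 to 24.

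**1. The plan's own figure.** SE = 0.185 × √(2/300) = 0.0151, and 0.05/0.0151 = 3.31. Power is 91.1% by noncentral t (91.2% by normal approximation). The stated power reproduces without entry week in the model.

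**2. With entry week added.** Residual SD = 0.185 × √(1 − R²), noncentral t, 300 per group:

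| Partial R² | Residual SD | Power |
|---|---|---|
| 0 | 0.1850 | 91.1% |
| 0.01 | 0.1841 | 91.3% |
| 0.02 | 0.1831 | 91.6% |
| 0.05 | 0.1803 | 92.4% |
| 0.10 | 0.1755 | 93.6% |

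At R² = 0.10 the SE falls by 1 − √0.90 = 5.1%. At 375 per group (750 in all, if every woman were evaluable) power goes from 95.9% to 97.4%.

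**3. Chance imbalance in entry week.** SD = 16/√12 = 4.62 weeks. SE of the arm difference = 4.62 × √(2/300) = 0.377 weeks, so the 95% limit is 1.96 × 0.377 = 0.74 weeks. The slope implied by a given R² is √R² × 0.185/4.62.
- R² = 0.01: 0.0040 per week; 0.0040 × 0.74 = 0.003 GI units, 6% of 0.05.
- R² = 0.10: 0.0127 per week; 0.0127 × 0.74 = 0.009 GI units, 19% of 0.05.

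**4. The imbalance is not a second cost.** Without the covariate, the 95% sampling error is 1.96 × 0.0151 = 0.0296. Removing the R² = 0.10 imbalance component gives √(0.0296² − 0.0094²) = 0.0281, which equals 0.0296 × √0.90. The possible shift and the lost precision are the same quantity, already inside the standard error.

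**5. How generous R² = 0.10 is.** A slope of 0.0127 over 16 weeks is a gradient of 0.20 GI units remaining after baseline adjustment. With an assumed mean GI of 1.0 (not given), that is the whole 20% rise, falling entirely within the entry window, with none of it absorbed by the baseline score.

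**6. Wording against model.** Protocol section 17 adjusts for baseline score only. The SAP 6.3 hypotheses add other demographic parameters. The SAP 6.3 model names baseline score, site, treatment and interactions. The hypothesis wording and the model therefore differ.

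**The case against.** The strongest case against is that nothing here is an error. Baseline plus site is a standard primary model and matches the protocol. Under randomisation, omitting a baseline covariate neither biases the comparison nor inflates the type I error. The planned power is reached without it, and the sample has since been raised to 750. Much of any stage effect is already handled: baseline score is in the model, randomisation balances on bleeding sites, and every entrant must already have at least 30 of them. All of this stands, and it limits the point to efficiency and prespecification.

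The mechanism is also less certain than it may look. The background describes an increase that persists or worsens; it does not say the rise is complete by week 24. If gingivitis worsened at a constant weekly rate, the change over a fixed three months would be the same whatever the entry week, and the covariate would gain little.

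Two stronger readings are tempting. A reader might take the 20% rise, spread it evenly over weeks 8 to 24 at an assumed mean GI of 1.0 to 1.4, and conclude that chance imbalance could move the estimate by 0.009 to 0.013, or 18 to 26% of the design difference. Those slopes imply R² of about 0.10 to 0.19 with no allowance for baseline adjustment; the documents support neither the plateau nor the size, and the shift lies within the ordinary sampling error of 0.030. A reader might also infer that the SAP promised adjustment for entry week specifically. It did not: its phrase is general, and SAP 5.1 lists pregnancy dating with the obstetrical variables.

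What remains is that entry week can be derived from data on file, has a stated rationale, and is already treated by the SAP as possibly relevant through its subgroup list.

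**Conclusion.** The point holds as a modest, nearly free improvement in precision, together with a wording mismatch to settle. The primary test is valid as planned, and its stated power is met at 91.1%. Over an assumed partial R² of 0 to 0.10, adding entry week takes power at 300 per group to at most about 93.6%. A chance imbalance at its 95% limit corresponds to at most about 0.009 GI units, which the standard error already reflects. Both figures rest on the assumed R²; the imbalance figure also rests on uniform entry. The true gain could be close to zero.

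One qualification applies to the reassurance from randomisation. The primary population is the evaluable one, defined partly by post-baseline visits and product supply (SAP 5.6.2), so it is not exactly the randomised set. A woman entering at week 24 reaches Month 3 near week 37, so entry week may affect who supplies data. That adds to the reasons for including it, but the documents do not quantify it and it does not demonstrate bias.

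**What to change.** Before the treatment blind is broken, amend SAP 6.3 as follows:

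1. Name gestational age at enrolment as a fixed covariate in the Löe-Silness, bleeding-site and pocket-depth ANCOVAs at every visit, retained whether or not it is significant. Use the four categories already in the SAP or a flexible continuous term, since the background does not support assuming a straight line. State which baseline dating record it is derived from.
2. Make the hypotheses match the model: list every adjustment variable, or delete the reference to other demographic parameters.
3. Keep the model without entry week as a sensitivity analysis, so that the result can be read against protocol section 18.

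The cost is a few lines of SAP text and one to three degrees of freedom. No new data are needed, and the subgroup analysis can stay.

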6.4 Birth Outcome Endpoints

Null Hypothesis: There is no difference between treatment groups with respect to the mean birth outcome when an adjustment is made for baseline demographic variables (e.g. smoking, evidence of preterm birth, etc.)

Alternative Hypothesis: There is a difference between treatment groups with respect to the mean birth outcome when an adjustment is made for baseline demographic variables (e.g. smoking, evidence of preterm birth, etc.)

Statistical analyses to determine treatment differences for mean Gestational Age and mean Birth weight will be analyzed using an analysis of variance (ANOVA) model with demographic factors such as previous pre-term birth (< 37 weeks; Y/N), self-reported smoking during pregnancy (Y/N), mother's weight at delivery (in grams), Study site and treatment. Interactions of these demographic variables with treatment will also be investigated for inclusion into the model. If the interactions are not significant at the 10% level then they will be eliminated from the final model. 95% confidence intervals will also be generated on the treatment difference of the mean gestational age and mean birth weight.

If any of the data does not satisfy the normality criterion, then transformations will be considered to improve normality or analogous nonparametric methods will be employed.

In addition, gestational age will be categorized as preterm (gestational age < 37 weeks) or term (gestational age \geq 37 weeks) for subsequent analyses and tested for treatment differences using logistic regression with the same demographic factors as described above. Gestational age will also be analyzed for treatment differences as a time-to-event variable using the log-rank test (and Kaplan Meier curves) and Cox Regression (adjusting for demographics/covariates). Other categorizations may also be used to identify early preterm births: 20 to < 34 weeks (early preterm), 34 to <37 weeks (late preterm), \geq 37 weeks; or low birth weight (< 2500 grams).

The distribution of birth weight will also be generated within the following gestational age categories (< 34, 34 to <35, 35 to <36, 36 to <37, 37 to <38, 38 to <39, \geq 39 weeks) for each treatment group using box plots.

Additional subgroups may be defined for analyzing birth outcome data, such as the following:

- By Study Site
- By Race (Caucasian, Black, Other)
- By Gestational Age at enrollment (8 to \leq 12 weeks, >12 to \leq 16 weeks, >16 to \leq 20 weeks, >20 to \leq 24 weeks)
- Women with no labor delay medication or procedures.
- By Age group (< median age vs. \geq median age)
- Pregnancy History (previous pregnancies (Y/N))

Additional analyses may also be performed in order to more fully understand the data.

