## Maternity Outcome (Record Review)

Maternity outcome data (plus ancillary variables such as birth weight) will be abstracted separately from medical records by trained personnel using standard methods. Maternal weight prior to delivery will be recorded. All maternity outcome data (including possible adverse events) will be collected from records by trained and qualified personnel who are blind to treatment assignment. A subject accountability form will be completed and subjects will be dismissed from the study. A subject accountability form will also be completed for subjects who drop out of the study prior to its completion.

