# 17. Hypotheses

Primary Hypothesis:

**Null Hypothesis**: There is no difference between treatment groups with respect to the mean Löe-Silness change from baseline score at each visit when an adjustment is made for the baseline Löe-Silness score.

Alternative Hypothesis: There is a difference between treatment groups with respect to the mean Löe-Silness change from baseline score at each visit when an adjustment is made for the baseline Löe-Silness score.

Secondary Hypothesis:

**Null Hypothesis:** There is no difference between treatment groups with respect to the mean gestational age when an adjustment is made for baseline demographic variables (e.g. smoking, evidence of preterm birth, etc.)

**Alternative Hypothesis**: There is a difference between treatment groups with respect to the mean gestational age when an adjustment is made for baseline demographic variables (e.g. smoking, evidence of preterm birth, etc.)

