The monthly gingivitis endpoints were the primary outcome measure, with the Month 3 evaluation being the primary time point of interest. Maternity outcome data (gestational age, birth weight, etc.) were abstracted separately from medical records as secondary variables with gestational age being of most importance. An interim analysis of the primary and secondary outcomes was performed by an independent statistician, and the target population size was adjusted. An independent Data and Safety Monitoring Board has assessed study design, conduct and outcomes at prescribed intervals with respect to study integrity, subjects' safety and evaluability.

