5.0. DATA COLLECTED AND EVALUABILITY

5.1 Demographic and Baseline Characteristic Measurements

The following general demographic variables were collected during this study: Age, Race, Marital Status, Education, Income, Employment and Insurance variables. Additional baseline obstetrical variables were collected: Last Menstrual Period, Estimated Delivery Date, In-vitro Fertilization, Date of first Ultra Sound and corresponding Gestational Age reading, Previous Pregnancy (full, preterm, abortions), Smoking Status during pregnancy, Alcohol Use during pregnancy, and Other drug use. Additional variables collected were the subject's height and weight at baseline and subject's weight at each monthly visit and at delivery. The subjects also took an oral hygiene questionnaire at the Baseline and Month 3 visits.

At Baseline each subject had a Loe-Silness Gingival Index exam taken, which was used to assess number of bleeding sites for inclusion into the study.

Gingival crevicular fluid, plaque bacteria and blood samples were taken at the Baseline visit and will be analyzed separately outside of this protocol by the study sites.

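### The birth-outcome models in SAP 6.4 adjust for the mother's weight at delivery, a post-randomisation variable, although the hypotheses specify baseline adjustment

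*SAP*

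**What the plan says.** SAP 6.4 lists the covariates for mean gestational age and mean birth weight as previous preterm birth, smoking during pregnancy and the mother's "weight at delivery (in grams), Study site and treatment". Two further provisions build on that list:

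- Preterm birth (under 37 weeks) is tested "using logistic regression with the same demographic factors as described above".
- "Interactions of these demographic variables with treatment will also be investigated for inclusion into the model", with terms dropped if not significant at the 10% level. This opens the door to a treatment-by-delivery-weight term.

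The Cox model is described only as adjusting for demographics or covariates, without naming them.

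The hypotheses are worded differently. Protocol 17 concerns "mean gestational age when an adjustment is made for baseline demographic variables". SAP 6.4 states its own hypotheses "when an adjustment is made for baseline demographic variables (e.g. smoking, evidence of preterm birth, etc".

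On timing, the Protocol's Maternity Outcome (Record Review) section says "Maternal weight prior to delivery will be recorded". SAP 5.1 lists the subject's "height and weight at baseline" as a separate item from weight at the monthly visits and at delivery.

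The interim model in SAP 3 also contained weight at delivery, there in pounds rather than grams. The change of unit alone does not alter the treatment estimate.

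**The concern.** Weight at delivery is measured after the subject has been randomised and has used the products. A longer pregnancy means more weight gained, and a heavier fetus adds directly to the mother's weight. The covariate is thus partly downstream of both outcomes. Holding it fixed removes part of any treatment effect that runs through gestation length or fetal weight. If treatment moved maternal weight by some other route, the model would show a gestational age difference that does not exist.

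The covariate lists are open (for example, Protocol 18 says its list is not exhaustive), so naming an extra covariate is not in itself a departure. The conflict is with the word baseline, and SAP 5.1 makes clear that delivery weight is not the baseline weight.

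At stake are the adjusted differences and 95% confidence intervals for birth weight and for gestational age. SAP 2 describes the maternity outcomes as "secondary variables with gestational age being of most importance", and gestational age supplied the sample size in Protocol 11.

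**Working it through.** **1. The plan's own figures.** Protocol 11: 300 per group, SD 4.1, difference 1.1 weeks. Power = Φ(1.1/4.1 × √(300/2) − 1.96) = 0.908, which agrees with the stated 90%.

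The interim table in SAP 3 gives the residual SD through SD = δ√(n/2)/(1.96 + 0.8416):

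- Gestational age, evaluable: δ = 1.143, n = 246 gives 4.52 weeks; δ = 0.953, n = 354 also gives about 4.52.
- Birth weight, evaluable: δ = 0.343 lb, n = 439 gives 1.81 lb.

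These SDs come from the mean square error of a model that already contains delivery weight.

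**2. Assumptions, because the documents give no weight SD, rate of gain or correlation.** Delivery weight W = W₀ + g × GA, with g = 0.5 to 1.5 lb per week and SD of W = 25 to 45 lb. Treatment affects W only through gestational age (GA).

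**3. Attenuation of the gestational age effect.** The correlation ρ between W and GA within arms is g·SD(GA)/SD(W). Taking 4.52 as the SD after adjustment, SD(GA) = 4.52/√(1 − ρ²), so ρ²(1 − ρ²) = (g × 4.52/SD(W))². The adjusted estimate is 1.143 × (1 − ρ²).

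| g (lb/week) | SD of W (lb) | ρ | Loss | Estimate (weeks) |
|---|---|---|---|---|
| 0.5 | 45 | 0.050 | 0.25% | 1.140 |
| 1.0 | 35 | 0.130 | 1.7% | 1.124 |
| 1.5 | 25 | 0.283 | 8.0% | 1.052 |

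The largest loss is 1.143 − 1.052 = 0.091 week, or 0.6 day.

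**4. Power.** With the covariate: Φ(1.143(1 − ρ²)/4.52 × √(n/2) − 1.96). Without it: Φ(1.143√(1 − ρ²)/4.52 × √(n/2) − 1.96).

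| Case | n per group | With | Without |
|---|---|---|---|
| Mildest | 300 | 87.1% | 87.1% |
| Middle | 300 | 86.1% | 86.7% |
| Worst | 300 | 81.3% | 84.4% |
| Worst | 375 | 89.0% | 91.3% |

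The evaluable target of about 600 is 300 per group; 375 per group is the enrolment ceiling of 750. A simulation of 4,000 runs in the worst case gave 81.5% and 84.5% at 300 per group. With no treatment effect on either variable, the covariate model rejected in 5.1% of runs at 300 per group and 4.9% at 375.

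**5. Weight raised by d, gestational age unaffected.** Bias = −(g·SD(GA)²/SD(W)²) × d.

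- g = 0.5, SD 45, d = 0.343 lb: −0.002 week.
- g = 1.0, SD 35, d = 2.0 lb: −0.034 week.
- g = 1.5, SD 25, d = 2.0 lb: SD(GA) = 4.52/√(1 − 0.080) = 4.71, so bias = −(1.5 × 4.71²/25²) × 2.0 = −0.107 week. The rejection rate is then 6.0% at 300 per group and 6.2% at 375.

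**6. Birth weight.** The coefficient of W is r × 1.81/SD(W), with r an assumed correlation between birth weight and W of 0.15 to 0.35. The loss is that coefficient times the rise in delivery weight, set against an effect of 0.343 lb.

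| r | SD of W (lb) | Rise in W (lb) | Loss (lb) | Loss (%) |
|---|---|---|---|---|
| 0.15 | 45 | 0.343 | 0.002 | 0.6 |
| 0.35 | 25 | 0.343 | 0.009 | 2.5 |
| 0.25 | 35 | 1.0 | 0.013 | 3.8 |
| 0.35 | 25 | 2.0 | 0.051 | 14.8 |

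Here 1.81 is treated as the unadjusted SD. If it is the SD after adjustment, as assumed for gestational age, the last row becomes 15.8%.

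**7. Outside the assumed range.** A correlation of 0.3 to 0.5 between W and GA would mean a loss of 9% to 25% (estimates 1.04 to 0.86 week). At 1.5 lb per week that needs a weight SD of about 24 down to 16 lb, so the conclusion does not rest on it.

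**The case against.** The strongest reply is that this hardly matters. The middle gestational age case loses 1.7% of the effect and under one point of power, and even the worst case stays above the 80% interim target. Type I error is about 5% if treatment affects neither variable. The outcomes are secondary, and the unadjusted log-rank test and Kaplan-Meier curves for gestational age, with the neonatal summaries in SAP 6.7, offer a view free of the covariate. All the sizes depend on assumed inputs, and nothing in the documents suggests that the products change maternal weight by another route. If normality fails, SAP 6.4 moves to a transformation or a nonparametric method, so the linear model sized here may not be the one reported.

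Most of this stands as a limit on size. It is also fair that the logistic preterm model has not been sized, that the linear results do not carry over automatically to an odds ratio, and that the Protocol does not say how long before delivery the weight is taken.

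It does not remove the point. The log-rank test and descriptive tables do not supply the planned adjusted differences and intervals, and a fallback analysis could keep the same covariate. No reason for using delivery weight is given, and no adjusted analysis without it is planned. Matching the interim model is no defence, since that model has the same feature.

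**Conclusion.** The concern holds and should be fixed. SAP 6.4 adjusts for a variable recorded after randomisation and partly determined by the outcomes, while the hypotheses specify baseline adjustment. The treatment coefficient in the gestational age, birth weight and preterm models is therefore not the hypothesised total effect.

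A gestational age effect acting through gestation length is attenuated. Any other treatment effect on weight would bias the estimate in a direction that depends on the pathway. Under the stated assumptions the distortion is probably small for both linear outcomes, with the larger birth weight figures arising only when extremes are combined. The case for acting rests on a mis-specified estimand for the leading secondary outcome and a cheap remedy, not on a large expected bias. The primary Löe-Silness analysis is not touched.

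**What to change.** Before unblinding, amend SAP 6.4 as follows:

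- Replace the mother's weight at delivery with maternal weight at baseline in the gestational age, birth weight and logistic models. The interaction screen then uses baseline weight too.
- Name the Cox covariates and leave delivery weight out.
- Keep the delivery-weight model only as a labelled sensitivity analysis.
- State that the final model differs on purpose from the interim model in SAP 3, whose mean square error produced the re-estimated sample size.

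The cost is SAP wording and one covariate in three model programs, plus the Cox specification. Baseline weight is recorded in the database at Visit 1 (Protocol 3, Baseline Visit 1; SAP 5.1).

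There are downsides. Residual variance may rise slightly. Baseline weight is taken anywhere from 8 to 24 weeks of pregnancy, so it mixes stages. Protocol 12 tied the interim error term to the SAP model, and the two will no longer match. Dropping weight altogether would also restore baseline-only adjustment, but baseline weight keeps some adjustment for maternal size.
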